9.2. Sample Size Considerations

9.2.1. Sample Size Assumptions

Sample size is largely based on feasibility; however, some justification is provided below.

Part 1a – Relative Bioavailability:

The sample size of 24 PK parameter population subjects will be used based on feasibility to address the objectives of Part 1a of the study.

There are no estimates for the coefficient of variation (CV) of HSWG for any PK parameters. An assumed CV of 27.5% for a PK parameter implies that the sample size of 24 PK parameter evaluable subjects will provide at least 80% power to demonstrate equivalence of the PK parameter. Equivalence is demonstrated when 90% confidence interval (CI) for the ratio of Test:Reference of the PK parameter will be within 0.8 to 1.25 following log transformation.

Two different test formulations are being used in this study. No adjustment for pre-planned multiple comparisons are made.

The total sample size of 27 subjects (9 subjects in 3 sequences) will be randomized to ensure 24 PK parameter evaluable subjects with PK parameter estimates from the reference and at least one test formulation.

Part 1b – Food Effect:

A sample size of 16 subjects will be randomized (8 per sequence) based on feasibility to address the objectives of Part 1b of the study.

This sample size will ensure equivalence (as specified in sample size assumption in Part 1a) with 80% power with an assumed CV of 22%.

Part 2 – Pharmacokinetics:

A sample size of approximately 10 subjects will be used in Part 2 based on feasibility to address the objectives of Part 2 of the study.

Part 3 – Pharmacokinetics - Fed State:

A sample size of 12 subjects (ideally 6 male, 6 female) will be randomized (10 active: 2 placebo) based on feasibility to address the objectives of Part 3 of the study.

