The log-transformed AUC(0-∞), AUC(0-t), and Cmax values for gepotidacin will be analyzed separately using a mixed effects model as appropriate to the study design, fitting fixed-effect terms for sequence, period, and regimen, and treating subject within sequence as a random effect. Point estimates and 90% CIs for the differences of interest (RC tablets and HSWG tablets versus capsules) will be constructed using the residual variance. Point and interval estimates will then be exponentially back-transformed to construct point and 90% CI estimates for the ratios of interest (RC tablets and HSWG tablets versus capsules).

Estimates of within-subject variability for AUC(0-∞), AUC(0-t), and Cmax of gepotidacin will be provided, where:

$$CVw (\%) = \text{sqrt}(\exp[MSE] - 1) \times 100$$

and MSE is the residual mean squared error from the model. CVw(%) represents a pooled measure of within-subject variability across regimens.

Distributional assumptions will be assessed by residual plots. Homogeneity of variance will be assessed by plotting the residuals against the predicted values from the model, whilst normality will be examined by normal probability plots. If assumptions are grossly violated, alternative analyses will be considered.

For the bioavailability assessment, Tmax will be analyzed nonparametrically using the Wilcoxon signed-rank test to compute the point estimate and 90% CI for the median difference for each comparison of interest.

For Parts 2 and 3, dose proportionality of AUC(0-∞) and Cmax will be explored separately and/or pooled together as a single model based on dose normalized parameters (log transformed parameters) using reference dose. The lower dose group (1500 mg) would be chosen as the reference dose.

The dose proportionality of AUC(0-∞) and Cmax will be summarized by descriptive statistics (including 90% confidence interval).

Detailed descriptions of the analyses in this study will be presented in the RAP.

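### Part 1a's stated 80% power is for one tablet-versus-capsule comparison with 24 subjects, but the 24 may have only one of the two tablets, and even 24 complete pairs give about 76%

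*Protocol*

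**What the plan says.** Protocol Section 9.2.1 (Part 1a) takes "An assumed CV of 27.5% for a PK parameter" and concludes that "the sample size of 24 PK parameter evaluable subjects will provide at least 80% power to demonstrate equivalence of the PK parameter". The criterion concerns one ratio: "Equivalence is demonstrated when 90% confidence interval (CI) for the ratio of Test:Reference of the PK parameter will be within 0.8 to 1.25". The assumed true ratio is not given.

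The same section then sets the enrolment: "The total sample size of 27 subjects (9 subjects in 3 sequences) will be randomized", in order "to ensure 24 PK parameter evaluable subjects with PK parameter estimates from the reference and at least one test formulation". Section 4.3 and the synopsis repeat that definition.

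The analysis in Protocol Section 9.4.1 makes two comparisons: "Point estimates and 90% CIs for the differences of interest (RC tablets and HSWG tablets versus capsules) will be constructed using the residual variance". SAP Section 7.1.3.2 codes them as separate B-versus-A and C-versus-A contrasts. On multiplicity, Section 9.2.1 says "No adjustment for pre-planned multiple comparisons are made". Neither Protocol Section 9.3.1 nor SAP Section 4 requires a member of the PK Parameter Population to have the capsule and both tablets. Replacement of subjects who discontinue is optional (Protocol Section 4.3).

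**The concern.** The power sentence and the enrolment sentence use the same number for two different counts. Power for one Test:Reference ratio depends on how many subjects have both the capsule and that tablet. The enrolment target counts anyone with the capsule and either tablet. A subject with capsule and RC but no HSWG counts toward the 24 and adds very little to HSWG versus capsule.

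This needs nothing unusual to happen. A subject in sequence ABC who misses Period 3 has no HSWG, and one in CAB who misses Period 3 has no RC; both still count. A BCA subject who misses Period 3 has no capsule and does not count. If losses fall unevenly, one tablet's interval is wider than the other's for a reason unrelated to its bioavailability, and a reader relying on the stated power would not expect that.

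**Working it through.** **Inputs.** CV 27.5%, limits 0.80 to 1.25, a 90% CI (one-sided 5% at each limit), 24 evaluable and 27 randomized, all from Section 9.2.1; sequences ABC, CAB, BCA from Section 4.1. The true ratio is not stated, so I use 1.00 (most favourable) and 0.95.

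**Step 1: the plan's own figure.** Log-scale within-subject SD: s = √ln(1 + 0.275²) = 0.270. Standard error of a treatment difference with 24 pairs: 0.270 × √(2/24) = 0.0779. Half-width of the limits: ln 1.25 = 0.2231, and 0.2231/0.0779 = 2.86.

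Normal approximation at ratio 1.00: 2Φ(2.86 − 1.645) − 1 = 77.7%. Exact power of the two one-sided tests:

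| Complete pairs | Residual df | Ratio 1.00 | Ratio 0.95 |
|---|---|---|---|
| 24 | 44 (three-period design) | 75.9% | 66.6% |
| 24 | 22 (two-period design) | 74.1% | 65.0% |
| 27 | 50 (three-period design) | 82.3% | 72.5% |
| 27 | 25 (two-period design) | 80.9% | 71.2% |

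So 80% is not reproduced at 24. At ratio 1.00 it needs 26 pairs (three-period df) or 27 (two-period df); at 0.95 it needs 33. Only a normal formula that treats equivalence as a single one-sided test exceeds 80% at 24 (88.8%), and that is not the stated criterion.

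**Step 2: effect of the definition.** I deleted tablet records from a 24-subject layout (8 per sequence), fitted subject, period and treatment by least squares, and took effective pairs as 2 divided by the contrast's variance factor. Here k subjects lack RC and another k lack HSWG, spread over the sequences; all 24 still count as evaluable. To separate the definition from Step 1, the last column lowers the CV to 26.4%, at which 24 complete pairs give exactly 80%.

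| k per tablet | Pairs per comparison | Effective pairs | Power, CV 27.5% | Power, CV 26.4% |
|---|---|---|---|---|
| 0 | 24 | 24.0 | 75.9% | 80.0% |
| 1 | 23 | 23.2 | 73.9% | 78.2% |
| 2 | 22 | 22.4 | 71.8% | 76.2% |
| 3 | 21 | 21.7 | 69.5% | 74.1% |

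The last column isolates the definition's cost: 80 − 78.2 = 1.8, 80 − 76.2 = 3.8 and 80 − 74.1 = 5.9 points. The pattern matters somewhat: 3 losses all in Period 3 of ABC give 68.7% for HSWG at CV 27.5% and leave RC at about 76%.

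**Step 3: starting from the 27 actually planned** (CV 27.5%, ratio 1.00).

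- 3 ABC subjects lose HSWG and 3 CAB subjects lose RC: 27 − 3 = 24 pairs in each comparison, 24.4 effective pairs, power 76.8%.
- 3 per sequence lose Period 3: the 3 BCA subjects have no capsule, so 27 − 3 = 24 still count as evaluable. Each comparison has 27 − 6 = 21 pairs, because the 3 BCA losses and 3 from one other sequence drop out. With all available records in the model there are 22.5 effective pairs and power is 72.0%. It is 69.2% if the 3 subjects without a capsule are left out.

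The second case shows the gap directly: the target of 24 is met exactly, yet each comparison has 21 pairs.

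**The case against.** The strongest reply is that little is at stake. Section 9.1 declares estimation without a formal hypothesis, and Section 9.2.1 calls the sample size largely a matter of feasibility. Subjects are healthy volunteers confined through Period 3, and 3 spare subjects are randomized. If no more than 3 of the 27 miss a period, both comparisons keep at least 24 pairs. The mixed model retains partly observed subjects, and the confidence interval will show whatever precision was achieved. All of this stands, and it limits the consequence. It does not make the power sentence right, because that sentence attaches a figure to a count that does not determine it.

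A reader might go further and infer three things that the documents do not support.

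- *Power could collapse to about 26%.* That is the arithmetic floor, with 12 subjects lacking RC and 12 lacking HSWG. Last-period dropout can remove at most 9 subjects per tablet, since only ABC loses HSWG and only CAB loses RC in Period 3.
- *Recruitment or replacement would stop once 24 subjects met the loose definition.* No section says so. The planned number is 27, and replacement is prompted by premature discontinuation.
- *The formulation choice or the decision on Part 1b was compromised.* Formulation choice rests on PK, safety and tolerability together, and no section makes 0.80 to 1.25 the rule for it or the meaning of similar bioavailability. Section 9.3.2 records that Part 1b was already judged unnecessary from Part 1a data.

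**Conclusion.** The point holds as a misstated power figure with two separable causes. First, at 24 complete pairs the power is about 74-76% at a true ratio of 1.00 and about 67% at 0.95 (three-period df), so the claim of at least 80% fails even with no missing data. Second, the evaluability definition allows fewer than 24 pairs per comparison, at a cost of about 2, 4 and 6 points for 1, 2 and 3 subjects lacking each tablet. Demanding 24 pairs per comparison would cure the second cause but not the first.

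The randomized number is adequate at ratio 1.00 if everyone completes (about 81-82% at 27). It falls to about 77% if 3 of the 27 lack each tablet, and to about 72% if 3 per sequence lose the last period.

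These figures assume that the CV of 27.5% is within-subject. They also assume that the stated power refers to each comparison separately, which is the natural reading of the criterion but is not said. The missing-data patterns are illustrative because the documents give no rate. The least-squares calculation ignores the small amount of between-subject information that a random-subject model can recover. Nothing here biases the ratios or invalidates their intervals.

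**What to change.** In Protocol Sections 9.2.1 and 4.3 and in the synopsis:

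- count a subject as evaluable for RC versus capsule, or for HSWG versus capsule, only with parameters for both the capsule and that tablet;
- state the true ratio assumed;
- replace the claim of at least 80% with the power at that number of pairs, about 76% at 24 pairs with ratio 1.00.

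In SAP Table 3.7 (Appendix 11), show the number of capsule-tablet pairs beside each ratio. The table shell is not reproduced in the SAP, so check first whether it already carries that count.

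This costs a few sentences and at most one column. No extra subjects are needed. The downside is a slightly less favourable stated power. Because Part 1a data were already available at Amendment 1, the gain now is an accurate record and report; it cannot change Part 1a enrolment.

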9.2.2. Sample Size Re-Estimation or Adjustment

Not applicable.

9.3. Data Analysis Considerations

In general, descriptive summaries will include number of subjects (n), mean, standard deviation (SD), median, minimum, and maximum for continuous variables; and percent for categorical variables. Summaries will present data by group, and where appropriate, by assessment time.

9.3.1. Analysis Populations

The **Safety Population** will consist of all subjects who receive at least 1 dose of study drug and have at least 1 postdose safety assessment.

The **PK Population** will consist of all subjects who received at least 1 dose of gepotidacin and have evaluable PK data for gepotidacin.

The **PK Parameter Population** will consist of all subjects in the PK Population, for whom valid and evaluable PK parameters were derived. This population will be used in the assessment and characterization of PK parameters.

9.3.2. Interim Analysis

No formal interim analyses are planned for this study. However, all preliminary safety, tolerability, and available PK data will be reviewed by the study team after completing Part 1a of the study to select the formulation for Part 1b, Part 2, and Part 3, and also to

determine if the effect of food on the selected formulation needs to be studied (Part 1b). At the time of finalization of Protocol Amendment 1, Part 1b is no longer needed based on data from Part 1a. The team will review unblinded data from Part 1a of this open-label study to select the appropriate formulation.

9.4. Key Elements of Analysis Plan

9.4.1. Primary Analyses

Pharmacokinetic Analyses

Plasma and urine concentrations of gepotidacin will be subjected to PK analyses using noncompartmental methods. Based on the individual concentration time data the following parameters will be estimated:

Plasma:

AUC(0-∞)	Area under the concentration-time curve (AUC) from time 0 (predose) extrapolated to infinite time
AUC(0-t)	Area under the concentration-time curve from time 0 (predose) to time of the last quantifiable concentration
Cmax	Maximum observed concentration
Frel	Relative bioavailability of drug, calculated as: [AUC(0-∞) _{tablet}]/[AUC(0-∞) _{capsule}] (Part 1a only)
t _{1/2}	Terminal phase half-life
t _{lag}	Lag time before observation of drug concentrations in sampled matrix
Tmax	Time to first occurrence of Cmax

Urine (Parts 1a, 2, and 3 only):

Ae total	Total unchanged drug (total amount of drug excreted in urine), calculated by adding all the fractions of drug collected over all the allotted time intervals
Ae(t ₁ -t ₂)	Amount of drug excreted in urine in time intervals of predose, 0 to 2 hours, 2 to 4 hours, 4 to 6 hours, 6 to 8 hours, 8 to 12 hours, 12 to 24 hours, 24 to 36 hours, and 36 to 48 hours for subjects
AUC(0-12)	Area under the concentration-time curve from time 0 (predose) to 12 hours after dosing
AUC(0-24)	Area under the concentration-time curve from time 0 (predose) to 24 hours after dosing
AUC(0-48)	Area under the concentration-time curve from time 0 (predose) to 48 hours after dosing
fe%	Percentage of the given dose of drug excreted in urine, calculated as: fe% = (Ae total/Dose) × 100
CL _r	Renal clearance of drug, calculated as: Ae total/AUC(0-t)

Plasma (all subjects) and urine (Parts 1a, 2, and 3 only) concentrations of gepotidacin and the associated PK parameters will be listed, and summary statistics (n, mean, median, SD, minimum, maximum, and CV) will be presented by day and treatment. Mean and individual plasma concentration versus time profiles will be presented graphically on linear and semilogarithmic scales.

The log-transformed AUC(0-∞), AUC(0-t), and Cmax values for gepotidacin will be analyzed separately using a mixed effects model as appropriate to the study design, fitting fixed-effect terms for sequence, period, and regimen, and treating subject within sequence as a random effect. Point estimates and 90% CIs for the differences of interest (RC tablets and HSWG tablets versus capsules) will be constructed using the residual variance. Point and interval estimates will then be exponentially back-transformed to construct point and 90% CI estimates for the ratios of interest (RC tablets and HSWG tablets versus capsules).

Estimates of within-subject variability for AUC(0-∞), AUC(0-t), and Cmax of gepotidacin will be provided, where:

$$CVw (\%) = \text{sqrt}(\exp[MSE] - 1) \times 100$$

and MSE is the residual mean squared error from the model. CVw(%) represents a pooled measure of within-subject variability across regimens.

Distributional assumptions will be assessed by residual plots. Homogeneity of variance will be assessed by plotting the residuals against the predicted values from the model, whilst normality will be examined by normal probability plots. If assumptions are grossly violated, alternative analyses will be considered.

For the bioavailability assessment, Tmax will be analyzed nonparametrically using the Wilcoxon signed-rank test to compute the point estimate and 90% CI for the median difference for each comparison of interest.

For Parts 2 and 3, dose proportionality of AUC(0-∞) and Cmax will be explored separately and/or pooled together as a single model based on dose normalized parameters (log transformed parameters) using reference dose. The lower dose group (1500 mg) would be chosen as the reference dose.

The dose proportionality of AUC(0-∞) and Cmax will be summarized by descriptive statistics (including 90% confidence interval).

Detailed descriptions of the analyses in this study will be presented in the RAP.

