- ^b A complete physical examination will include at a minimum, assessment of the cardiovascular, respiratory, gastrointestinal, and neurological systems. Height and weight will also be measured and recorded. A brief physical examination will include, at a minimum, assessments of the skin, lungs, cardiovascular system, and abdomen (liver and spleen).
- ^c Triplicate 12-lead ECGs will be measured in semi-supine position after 5 minutes rest and obtained at least 5 minutes apart on Day -1. Single 12-lead ECGs will be measured in semi-supine position after 5 minutes rest at all other time points during the study
- ^d Single vital signs will be measured in semi-supine position after 5 minutes rest and will include systolic and diastolic blood pressure, and heart rate. Body temperature and respiratory rate will be collected at Screening only.
- ^e Safety laboratory tests include serum chemistry, hematology, and urinalysis.
- ^f Subjects will fast from food and drink (except water) for at least 10 hours before study drug administration on Day 1 of each period. For the fed group of the food effect evaluation in Part 1b, study drug will be administered within 30 minutes after the completion of a moderate fat meal. For Part 3, study drug will be administered within 30 minutes after completion of a standard Japanese meal.
- ^g Urine collection intervals (Parts 1a, 2, and 3 only) for subjects include 0 (predose), 0 to 2 hours, 2 to 4 hours, 4 to 6 hours, 6 to 8 hours, 8 to 12 hours, 12 to 24 hours, 24 to 36 hours, and 36 to 48 hours.
- ^h For subjects who consent only: collect 1 pharmacogenetic sample after the start of dosing (preferably Day 1). Informed consent for optional pharmacogenetics research must be obtained before collecting a sample.
- ⁱ For Parts 1a and 3, subjects will be discharged from the clinical research unit on Day 3 of Period 3. For Parts 1b and 2, subjects will be discharged on Day 3 of Period 2.

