DNCmax	Dose normalized maximum observed concentration (Part 2 and Part 3 for use in the pooled analysis with Part 2), to be calculated as

Parameter	Parameter Description
	DNCmax = Cmax / Dose

NOTES:

- Additional parameters may be included as required.

Table 5 Derived Urine Pharmacokinetic Parameters (Parts 1a, 2, and 3 only)

Parameter	Parameter Description
Ae total	Total unchanged drug (total amount of drug excreted in urine), calculated by adding all the fractions of drug collected over all the allotted time intervals
Ae(t1-t2)	Amount of drug excreted in urine in a time intervals for predose, 0 to 2 hours, 2 to 4 hours, 4 to 6 hours, 6 to 8 hours, 8 to 12 hours, 12 to 24 hours, 24 to 36 hours, and 36 to 48 hours.
AUC(0-12)	Area under the urine concentration-time curve over time 0 (predose) to 12 hours after dosing. The AUC will be calculated by the linear trapezoidal rule based on the urine concentration data from each collection interval versus the corresponding urine collection interval.
AUC(0-24)	Area under the urine concentration-time curve over time 0 (predose) to 24 hours after dosing. The AUC will be calculated by the linear trapezoidal rule based on the urine concentration data from each collection interval versus the corresponding urine collection interval.
AUC(0-48)	Area under the urine concentration-time curve over time 0 (predose) to 48 hours after dosing. The AUC will be calculated by the linear trapezoidal rule based on the urine concentration data from each collection interval versus the corresponding urine collection interval.
fe%	Percentage of the given dose of drug excreted in urine, calculated as: $fe\% = (Ae\ total / Dose) \times 100$
CLr	Renal clearance of drug, calculated as: $CLr = Ae\ total / AUC(0-t)$

NOTES:

- Additional parameters may be included as required.

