	
information (and can erroneously indicate that absolutely no drug is present)
 
 for summary statistics these are set to 0 (to avoid skewing of the summary statistics) Individual NQs which fall between two measurable concentrations are set to missing (individual values of this nature are assumed to be an anomaly) If two or more NQ values occur in succession between measurable concentrations, the profile will be deemed to have terminated at the last measurable concentration prior to these NQs. For the purpose of individual subject plots, these NQs will be set to 0, and the subsequent measurable concentrations will be retained. For the derivation of pharmacokinetic parameters, these NQs and any subsequent measurable concentrations will be omitted (set to missing).
Reporting of Pharmacokinetic Parameters	
Descriptive Summary Statistics. (Log Transformed)	
N, n, geometric mean, 95% CI of geometric mean, standard deviation (SD) of logged data and between subject coefficient of variation (CV_b (%)) will be reported.
 $CV_b (\%) = \sqrt{(\exp(SD^2) - 1) * 100}$ 
[NOTE: SD = SD of log transformed data]

Parameters Not Being Log Transformed	T _{max} , first point, last point and number of points used in the determination of λ _z .
Parameters Not Being Summarised	Additionally include t _{max} , first point, last point and number of points used in the determination of λ _z .
Listings	Include the first point, last point and number of points used in the determination of λ _z .
Graphical Displays	

 Refer to IDSL Statistical Principals 7.01 to 7.13. 	

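### Renal clearance divides urinary drug summed to 48 h by plasma AUC to the last quantifiable time, so the two windows can differ and CLr can be off by a few percent

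*Protocol*

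**What the plan says.** Protocol 9.4.1 gives CLr as "Renal clearance of drug, calculated as: Ae total/AUC(0-t". SAP 7.1.3.1, Table 5, under "Renal clearance of drug, calculated as", gives the same ratio.

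- **Numerator.** Ae total is "calculated by adding all the fractions of drug collected over all the allotted time intervals". The Time and Events footnote (Protocol 7.1) ends the urine intervals with "24 to 36 hours, and 36 to 48 hours". The Ae(t1-t2) entry begins "Amount of drug excreted in urine in time intervals of predose, 0 to 2 hours", so predose heads the list of intervals; SAP Table 5 also lists it. SAP Listing 45 (10.11.8) names only Ae(0-2) through Ae(36-48).
- **Denominator.** AUC(0-t) is the "Area under the concentration-time curve from time 0 (predose) to time of the last quantifiable concentration", so its end point belongs to each profile. SAP 10.3.3 drops non-quantifiable (NQ) values at the end of a profile. Where two or more successive NQs lie between measurable values, "the profile will be deemed to have terminated at the last measurable concentration prior to these NQs".
- **No matching rule.** Neither document cuts Ae at t or defines a plasma AUC(0-48). The SAP's AUC(0-48) is an area under the urine concentration curve.
- **Role.** Protocol Section 3 lists CLr among the primary urine endpoints for Parts 1a, 2 and 3. SAP Table 3 (7.1.1) plans summaries and listings of urine parameters, and no model.

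**The concern.** Renal clearance is the amount excreted over an interval divided by the plasma AUC over that same interval. Here the numerator is fixed at 48 h and the denominator floats. When the last quantifiable plasma sample is at 36 h or 24 h, the ratio credits urine excreted after t to plasma exposure that ends at t, and CLr comes out too high. A missed 48 h blood draw is enough to cause this, whatever the assay limit. The reverse also holds: if a late urine collection is missed and plasma runs to 48 h, CLr comes out too low.

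What is at stake is the accuracy of a primary parameter tabulated by treatment. A secondary question is whether the predose void, which in Periods 2 and 3 may hold drug from the previous dose, is meant to be part of Ae total, since Ae total feeds both CLr and fe%.

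**Working it through.** The documents give no figure for CLr, so there is nothing to reproduce. The check is how far the stated ratio departs from a matched one.

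**Formula.** If renal clearance is constant over time and urine is complete to 48 h, Ae(0-48) = CLr × AUC(0-48). The planned ratio then has relative error AUC(0-48)/AUC(0-t) − 1. With f(t) the share of AUC(0-∞) lying beyond time t, this equals (1 − f(48))/(1 − f(t)) − 1. With a 12 h half-life, f halves every 12 h after 12 h.

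**Inputs** (Protocol 4.5, Table 5, 1500 mg): half-life 12.0 h; single-dose AUC(0-∞) 20.1; Day 14 AUC(0-12) 22.4; accumulation ratio Ro 1.30.

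**Route A: f(12) from Ro alone.** f(12) = 1 − 1/1.30 = 0.231. Then f(24) = 0.115, f(36) = 0.058, f(48) = 0.029.
- t = 36 h: 0.971/0.942 − 1 = 3.1%
- t = 24 h: 0.971/0.885 − 1 = 9.8%

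This route takes steady-state AUC(0-12) to equal single-dose AUC(0-∞). Table 5 gives 22.4 against 20.1, so it leans high.

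**Route B: f(12) from Table 5's AUCs, reading Ro as the AUC(0-12) ratio (an assumption).** Day 1 AUC(0-12) = 22.4/1.30 = 17.2. f(12) = 1 − 17.2/20.1 = 0.143. Then f(24) = 0.071, f(36) = 0.036, f(48) = 0.018.
- t = 36 h: 0.982/0.964 − 1 = 1.9%
- t = 24 h: 0.982/0.929 − 1 = 5.8%

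**Route C: two-phase oral profiles** fitted approximately to the AUC, Cmax, Tmax and half-life in Protocol Tables 5 to 7, with the terminal phase assumed to carry 10 to 40% of AUC.
- t = 36 h: 0.6 to 2.8%
- t = 24 h: 1.9 to 9.0%

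**Ceiling.** One-phase decline at 12 h would give 7.1% (t = 36 h) and 25% (t = 24 h). The protocol's figures do not fit it: Cmax × half-life/ln 2 = 4.08 × 12/0.693 = 70.6, against a stated AUC of 20.1.

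**Opposite direction.** If the 36 to 48 h urine is missed and plasma runs to 48 h, the error is (1 − f(36))/(1 − f(48)) − 1: 0.942/0.971 − 1 = −3.0% (route A) or 0.964/0.982 − 1 = −1.8% (route B).

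**Does t fall short of 48 h?** Route C puts plasma at 48 h at about 5 to 31 ng/mL after 1500 mg and 11 to 41 ng/mL after 3000 mg. Protocol 7.4.3 refers to the approved bioanalytical method without a quantification limit, so these levels cannot be classed as quantifiable or not.

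**Predose void.** Assume a 10 h void covering 62 to 72 h after the previous dose, at equal doses. Route A gives 0.231 × (2^(−50/12) − 2^(−60/12))/0.971 = 0.6% of Ae total, and 0.24 to 0.98% for half-lives of 8.66 to 16 h. Route C gives 0.1 to 0.5%. In Period 1 it is zero. In Part 2 the previous dose is 1500/3000 = 50% of the current one; in Part 3 it is 1500/2250 = 67%, then 2250/3000 = 75%. The effect shrinks in proportion.

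**The case against.** The strongest reply is that the trigger is not shown. Blood and urine are both scheduled to 48 h, and if the 48 h plasma sample is quantifiable the stated ratio is already matched. That stands, and it makes the error conditional.

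The rule on successive NQs adds little. After 12 h the plasma samples are at 24, 36 and 48 h, so the rule would shorten the late profile only if 24 and 36 h were both NQ with 48 h measurable, which is unlikely in a declining curve. Trailing NQs and missed draws are the realistic routes.

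It is also true that no modelled result uses CLr, and that a shift of a few percent is small beside the 16.2 to 28.8% between-subject CVs for AUC in Protocol Table 6. That limits the consequence but does not make the formula right.

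A reader might infer more: that t is shorter at lower exposure, so CLr is inflated at 1500 mg relative to 3000 mg, or for the less bioavailable formulation, giving a false trend. The documents do not support this as a statement of fact. It needs an assay limit that truncates 1500 mg profiles more often, and no limit is given.

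Nor is CLr overstated every time plasma ends early; that also needs complete late urine with measurable drug in it.

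Finally, the predose void is not a material bias. It is below about 1%, Listing 45 already leaves it out, and the Part 1a Latin square balances periods across formulations. In Parts 2 and 3 it would raise CLr at the higher doses, against the supposed low-dose inflation.

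**Conclusion.** The definition is wrong as written, but the error is minor. Whenever the urine and plasma windows differ, the stated ratio is not renal clearance over any single interval. With plasma ending early and later urine collected and containing drug, the overstatement is about 1 to 3% at t = 36 h and 2 to 10% at t = 24 h. With plasma quantifiable at 48 h and urine complete it is zero, and with late urine missed it is negative.

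The sizes rest on a terminal half-life near 12 h, constant renal clearance, and a terminal share of AUC that the documents do not state directly. The frequency, and any imbalance by dose or formulation, rest on an assay limit that is not given and remain unknown. The place of the predose sample in Ae total is a wording point worth settling at the same time, with an effect under about 1%.

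**What to change.** In Protocol 9.4.1 and SAP Table 5, define CLr = Ae(0-t*)/AUC(0-t*), where t* is the latest urine-interval end up to which urine collection is complete and plasma is quantifiable. When both run to 48 h, t* is 48 h. This handles early plasma termination and missed late urine alike.

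As a minor clarification in the same entries, define Ae total as the sum of the post-dose 0 to 48 h intervals only, consistent with SAP Listing 45, with the predose sample reported but not summed.

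The cost is a few lines of wording and one partial-AUC setting in the noncompartmental software, with no new samples. CLr will be slightly lower for profiles whose plasma ends early.
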